4 INTRODUCTION

This SAP has been developed after review of the clinical study protocol (Final Version 1.0 dated 25 June 2018) and protocol amendment Version 3 dated 12 December 2018.

This SAP describes the planned analysis of the safety, tolerability and PK data from this study. A detailed description of the planned TFLs to be presented in the Clinical Study Report (CSR) is provided in the accompanying TFL shell document.

The intent of this document is to provide guidance for the statistical analyses of PK data. In general, the analyses are based on information from the protocol, unless they have been modified by agreement between BeiGene, Ltd. and Covance Early Clinical (EC) Biometrics. A limited amount of information concerning this study (eg, objectives, study design) is given to help the reader's interpretation. This SAP must be finalized prior to the lock of the clinical database for this study. When the SAP and TFL shells are agreed upon and finalized, they will serve as the template for this study's CSR.

This SAP supersedes the statistical considerations identified in the protocol; where considerations are substantially different, they will be so identified. If additional analyses are required to supplement the planned analyses described in this SAP, they may be performed and will be identified in the CSR. Any substantial deviations from this SAP will be agreed upon between BeiGene, Ltd. and Covance EC Biometrics and identified in the CSR.

This SAP is written with consideration of the recommendations outlined in the International Conference on Harmonisation (ICH) E9 guideline entitled, "Guidance for Industry: Statistical Principles for Clinical Trials" and the ICH E3 guideline entitled, "Guidance for Industry: Structure and Content of Clinical Study Reports."^{1,2}

5 STUDY OBJECTIVES

5.1 Primary Objectives

- To assess the disposition of [14C]-pamiparib following oral administration of a single 60 mg (~100 μCi) dose in patients with advanced and/or metastatic solid tumors
- To assess the plasma PK of total radioactivity and pamiparib following a single oral dose of [14C]-pamiparib
- To determine the whole blood and plasma concentrations of total radioactivity
- To determine the urinary and faecal recovery of total radioactivity

5.2 Secondary Objectives

- To characterize and identify metabolites of [14C]-pamiparib in plasma, urine, and feces
- To determine plasma and urine concentrations of pamiparib and/or its major metabolites
- To assess the safety and tolerability of pamiparib during the treatment phase

6 STUDY DESIGN

This is an open-label, inpatient study in patients with advanced and/or metastatic solid tumors, which consists of 2 parts: a research phase and a treatment phase.

[figure not shown]
An overview of the study design for Part 1 and Part 2 is shown in Figure 1 and Figure 2, respectively.

Potential patients will be screened to assess their eligibility to enter the study within 28 days prior to the first dose administration. Re-screening of patients will be allowed per the Principal Investigator's (PI's) discretion. Up to approximately 10 patients will be enrolled to ensure 4 patients complete Part 1 of the study.

The start of the study is defined as the date the first enrolled patient signs an Informed Consent Form (ICF). The point of enrollment occurs at the time of patient number allocation. The end of the study is defined as the date of the last patient's last assessment (scheduled or unscheduled) or follow-up.

6.1 Study Part 1 (Research Phase)

Figure 1: Study Schematic: Part 1

Abbreviation: CRU = Clinical Research Unit.

Patients will be admitted into the Clinical Research Unit (CRU) on Day -1. On the morning of Day 1, patients will receive a single oral dose of 60 mg containing approximately 100 μCi $(3.7 \text{ MBq}) \text{ of } [^{14}\text{C}]$ -pamiparib.

^{1.} Discharge may occur earlier than Day 7 if discharge criteria have been met (approximately 90% mass balance recovery, or < 1% of total dose recovered in urine and feces for 2 consecutive 24-hour collection intervals).

² Patients will attend a Follow-up visit within 7 days of Discharge (if discharged on Day 7 or before), or within 7 days of their final non-residential visit (if additional non-residential visits are required).

Patients will be resident at the CRU until completion of all assessments on Day 7, but may be discharged earlier at the PI's discretion if they meet the following discharge criteria:

• Approximately 90% of the radioactive dose is recovered

or

• < 1% of the radioactive dose is recovered in urine and feces for 2 consecutive 24-hour collection intervals

[figure not shown]
If the discharge criteria have not been met on Day 7, patients may be asked to collect 24-hour excreta samples for up to a further 7 days (up to Day 14) on a non-residential basis. Patients may be required to remain resident at the CRU for longer than 7 days if deemed necessary by the PI to ensure patient safety. If the discharge criteria have not been met by Day 14, the need for additional sample collection will be at the discretion of the PI.

Patients experiencing emesis during the first 4 hours postdose may not be evaluable and therefore may be discharged on the same day from the clinical site, provided there are no safety concerns, and after discharge study procedures are performed. These patients will attend a Follow-up visit within 7 days of Discharge and may be enrolled to Part 2 of the study at the discretion of the PI. Patients may be prescribed anti-emetics if required.

A Follow-up visit will occur within 7 days of Discharge from the CRU (if discharged on Day 7 or before), or within 7 days of the patients' final non-residential visit (if additional non-residential visits are required). During the Follow-up visit, the patients may be entered into Part 2 of the study if deemed appropriate by the PI.

6.2 Study Part 2 (Treatment Phase)

Figure 2: Study Schematic: Part 2

Patients will undergo safety assessments ≤ 7 days prior to the start of pamiparib treatment in Part 2. These assessments may be conducted at the Follow-up visit for Part 1 if it occurs within

this time window, or at a separate site visit. If there are greater than 8 weeks between tumor assessments at study Screening and the planned start of pamiparib treatment in Part 2, patients should undergo a computed tomography (CT) scan prior to the start of treatment in Part 2.

During Part 2, patients will attend 2 site visits per cycle during Cycles 1 and 2, and 1 site visit per cycle during each subsequent cycle. Patients will continue receiving treatment until occurrence of progressive disease, unacceptable toxicity, pregnancy, death, withdrawal of consent, lost to follow-up, major protocol violation which in the opinion of the Sponsor would have significant impact on the study or its outcome, start of new anticancer therapy, withdrawal by the PI, or study termination by Sponsor. Patients will attend an end-of-treatment (EOT) visit within 7 days following their last dose and a safety Follow-up visit approximately 30 days after the last dose of pamiparib.

The reason for treatment discontinuation will be recorded on the electronic Case Report Form (eCRF). An EOT visit should occur within 7 days after the final pamiparib dose. The visit should be scheduled as soon as possible, but the EOT visit may occur later after discussion with the Medical Monitor for specific circumstances, such as prolonged hospitalization. Every effort must be made to encourage the patient to complete their EOT visit and appropriate safety follow-ups.

TREATMENTS

The following is a list of the study treatment abbreviations and ordering that will be used in the TFLs.

Part	Study Treatment Name
1	60 mg [¹⁴ C]-pamiparib
2	60 mg pamiparib BID

8 SAMPLE SIZE JUSTIFICATION

No formal statistical assessment of sample size has been conducted. The sample size chosen for this study is common in human radiolabeled studies and is considered sufficient to achieve the objectives of the study. Up to approximately 10 patients will be enrolled and studied in order that 4 patients complete Part 1 of the study.

9 DEFINITION OF ANALYSIS POPULATIONS

The Safety Population for part 1 will consist of all patients who received at least 1 dose of study drug, 60 mg [¹⁴C]-pamiparib in Part 1.

The Safety Population for part 2 will consist of all patients who received at least 1 dose of 60 mg pamiparib in Part 2.

The **PK Population** will consist of all patients who received at least 1 dose of study drug (60 mg [¹⁴C]-pamiparib, and have evaluable PK data. A patient will be excluded from the PK summary statistics and statistical analysis if the patient has an adverse event (AE) of vomiting that occurs at or before 2 times median time to maximum concentration (t_{max}).

All protocol deviations that occur during the study will be considered prior to database lock for their severity/impact and will be taken into consideration when patients are assigned to analysis populations. Details of patient assignment to the analysis populations will be listed.

STATISTICAL METHODOLOGY 10

10.1 General

Data listings will be provided for the Safety Population. Summary statistics and statistical analyses will be performed for patients included in the relevant analysis populations (Safety/PK).

For continuous data, summary statistics will include the arithmetic mean, arithmetic standard deviation, median, minimum, maximum, and number. For log-normal data (eg, the PK parameters: areas under the concentration-time curve [AUCs] and maximum observed concentration [C_{max}]), the geometric mean and geometric coefficient of variation (CV%) will also be presented. For categorical data, frequency counts and percentages will be presented. Data listings will be provided for all patients up to the point of withdrawal, with any patients excluded from the relevant population highlighted. For the calculation of summary statistics and statistical analysis, unrounded data will be used.

Missing values will not be imputed.

Data analysis will be performed using SAS® Version 9.4 or higher.

Analysis Data Model (ADaM) datasets will be prepared using Clinical Data Interchange Standards Consortium (CDISC) ADaM Version 2.1, and CDISC ADaM Implementation Guide Version 1.1. Pinnacle 21 Community Validator Version 2.2.0 will be utilized to ensure compliance with CDISC standards.

10.1.1 Definition of Baseline and Change from Baseline

Baseline for each parameter is in each part defined as the last value measured prior to dosing for that part i.e. Baseline for Part 1 is to be the last value prior to dosing for Part 1 and for Part 2, last value prior to the 1st dose in Part 2, including repeat (vital signs and electrocardiograms [ECGs]) and unscheduled (clinical laboratory parameters) readings (see Section 10.1.2 for definitions of repeat and unscheduled readings). For ECGs taken in triplicate, baseline will be the mean of the last 3 values taken prior to dosing.

Mean change from baseline is the mean of all individual patient's change from baseline values. Each individual change from baseline will be calculated by subtracting the individual patient's baseline value from the value at the timepoint. The individual patient's change from baseline

Statistical Analysis Plan Covance Study: 8381180

values will be used to calculate the mean change from baseline using a SAS procedure such as Proc Univariate.

10.1.2 Repeat and Unscheduled Readings

Repeat readings occur when the original vital signs or ECG result requires confirmation. Repeat readings are labelled as 'Repeat' in the listings and replace the original readings in all summaries and changes from baseline presentations and calculations. Prior to dosing, all readings taken in addition to the original reading are defined as predose repeats. Postdose repeat readings are defined as readings collected within 15 minutes of the actual time of the original reading. Where results are taken in triplicate and repeated, the last 3 readings are used in all subsequent calculations.

With the exception of predose results described above, unscheduled readings for vital signs or ECGs are defined as readings collected >15 minutes from the actual time of the original reading. Where results are taken in triplicate, the original reading is defined as the first reading of the triplicate. All results not taken at a scheduled timepoint for other data types (eg, clinical laboratory parameters) are unscheduled. Unscheduled readings are labelled as 'Unscheduled' in the listings. Because unscheduled readings are not associated with any scheduled timepoint, they are excluded from all summaries (with the exception that they may be used as baseline, as stated in Section 10.1.1).

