2.2.2. Secondary Endpoints

The metabolite outcome endpoints will be derived:

- Metabolic profile of pamiparib
- Identification of pamiparib metabolites.

The secondary safety outcome measures are as follows:

- Incidence and severity of AEs
- Incidence of laboratory abnormalities, based on hematology and clinical chemistry test results

CONFIDENTIAL

Protocol Reference: BGB-290-106

- 12-lead ECG parameters
- Vital sign measurements
- Physical examinations.

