3.1.2. Study Part 2 (Treatment Phase)

Figure 4: Study Schematic: Part 2

Abbreviations: BID = twice daily; CRU = Clinical Research Unit.

Patients will undergo safety assessments ≤ 7 days prior to the start of pamiparib treatment in Part 2. These assessments may be conducted at the Follow-up visit for Part 1 if it occurs within this time window, or at a separate site visit. If there are greater than 8 weeks between tumor assessments at study Screening and the planned start of pamiparib treatment in Part 2, patients should undergo a computed tomography (CT) scan prior to the start of treatment in Part 2.

During Part 2, patients will attend 2 site visits per cycle during Cycles 1 and 2, and 1 site visit per cycle during each subsequent cycle. Patients will continue receiving treatment until occurrence of progressive disease (PD), unacceptable toxicity, pregnancy, death, withdrawal of consent, lost to follow-up, major protocol violation which in the opinion of the Sponsor would have significant impact on the study or its outcome, start of new anticancer therapy, withdrawal by the PI, or study termination by Sponsor. Patients will attend an End-of-treatment (EOT) visit within 7 days following their last dose and a safety Follow-up visit approximately 30 days after the last dose of pamiparib.

The reason for treatment discontinuation will be recorded on the electronic Case Report Form (eCRF). An EOT visit should occur within 7 days after the final pamiparib dose. The visit should be scheduled as soon as possible, but the EOT visit may occur later after discussion with the

12 December 2018 Page 27 of 72

Medical Monitor for specific circumstances, such as prolonged hospitalization. Every effort must be made to encourage the patient to complete their EOT visit and appropriate safety follow-ups.

CONFIDENTIAL

Protocol Reference: BGB-290-106

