10.5.3 Clinical Laboratory Parameters

Clinical chemistry and hematology data will be summarized by part and parameter. In addition, all clinical chemistry, hematology, and urinalysis data outside the clinical reference ranges will be listed by part and parameter.

Values for any clinical chemistry, hematology, and urinalysis values outside the clinical reference ranges will be flagged on the individual patient data listings.

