10.5.5 Electrocardiogram

The ECG data will be obtained directly from the 12-lead ECG traces. These data include the QT interval calculated using the Fridericia correction (QTcF), the PR and QT intervals, the QRS duration, and heart rate.

Where ECGs are measured in triplicate (at approximately 2-minute intervals), the mean value will be used in all subsequent calculations. Changes from baseline will be calculated.

Values for ECG parameters outside the clinical reference ranges will be flagged on the individual patient data listings.

Statistical Analysis Plan Covance Study: 8381180 Sponsor Reference: BGB-290-106

The ECG data will be summarized by part. Change from baseline will also be summarized for Part 1.

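### The secondary endpoint on incidence of laboratory abnormalities has no specified analysis in the SAP, and the rule on unscheduled readings would remove unscheduled labs from any table that supplied one

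*SAP*

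**What the plan says.** Protocol 2.2.2 lists as a secondary safety endpoint: "Incidence of laboratory abnormalities, based on hematology and clinical chemistry test results". It stands as an item separate from the incidence and severity of adverse events.

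For laboratory data, SAP 10.5.3 says: "Clinical chemistry and hematology data will be summarized by part and parameter". It adds that "all clinical chemistry, hematology, and urinalysis data outside the clinical reference ranges will be listed by part and parameter", and that such values are flagged in the individual listings. SAP Section 12 reports no departures from the protocol's analyses.

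SAP 10.1.2 applies its rule to labs by name: "All results not taken at a scheduled timepoint for other data types (eg, clinical laboratory parameters) are unscheduled". Such results are kept in the listings ("Unscheduled readings are labelled as 'Unscheduled' in the listings") but not in tables: "Because unscheduled readings are not associated with any scheduled timepoint, they are excluded from all summaries". SAP 10.1.1 allows one use outside the listings, as a baseline.

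On visit frequency in Part 2, Protocol 3.1.2 says that "patients will attend 2 site visits per cycle during Cycles 1 and 2, and 1 site visit per cycle during each subsequent cycle".

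For ECGs, SAP 10.5.5 summarises the data by part but limits the summary of change: "Change from baseline will also be summarized for Part 1".

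**The concern.** An incidence is a count of patients over a denominator. The SAP names no such count for the laboratory endpoint: no table of abnormal versus normal, no CTCAE laboratory grade table, no worst-value table and no shift table. The rule on unscheduled readings makes this worse. Anyone who adds an incidence table while following SAP 10.1.2 must leave out samples drawn between visits, and those are the samples likely to be taken while a toxicity is being followed.

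Safety and tolerability in the treatment phase is a secondary objective. At stake is whether the report gives an estimate for an endpoint that the protocol names, and whether the laboratory tables show each patient's worst value.

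**Working it through.** The plan gives no figure to reproduce. Protocol 9.1 has no formal sample size calculation, and neither document gives an expected rate of laboratory abnormalities. The check compares sections and adds some schedule arithmetic.

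**1. Endpoint against planned output.** SAP 10.1 gives mean, standard deviation, median, minimum, maximum and number for continuous data. Minimum and maximum show the most extreme value in the group, not how many patients had an abnormality. SAP 10.1 also promises counts and percentages for categorical data, but 10.5.3 defines no categorical laboratory variable to which that could apply.

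**2. Scheduled Part 2 labs** (28-day cycles; Appendix 4 schedule: Days 1 and 15 in Cycles 1 and 2, Day 1 thereafter).
- Study-treatment days: 1, 15, 29, 43, 57, 85, 113 and so on.
- Gaps: 14 days up to Day 57, then 28 days.
- With the ±2-day window at both ends: 14 − 4 = 10 to 14 + 4 = 18 days, then 28 − 4 = 24 to 28 + 4 = 32 days.

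**3. Resolution times in Protocol Table 3.** Limits are 7 days (for example Grade 3 neutropenia and Grade 3 thrombocytopenia) or 14 days (for example Grade 3 anemia and Grade 3 transaminase elevation). Table 3 does not say when the clock starts, so I assume it starts at the scheduled lab that prompts the hold.
- 7 < 10: the next scheduled lab cannot show resolution within 7 days in any cycle.
- 14 < 24: from Cycle 3 it cannot show resolution within 14 days.
- 14 lies inside 10 to 18: in Cycles 1 and 2 it may or may not.

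If the abnormality is instead found between visits, the lab that found it is itself unscheduled. Either way, unscheduled labs are foreseeable.

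**4. Blood volume allowance (Appendix 2).** One panel is 4.7 + 2.7 + 2.7 = 10.1 mL. Two per cycle in Cycles 1 and 2 make 20.2 mL, which leaves 40 − 20.2 = 19.8 mL under the cap for extra samples. That covers one further full panel (19.8 / 10.1 = 1.96) or seven hematology samples (19.8 / 2.7 = 7.3). The protocol therefore provides for extra draws.

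**5. Where a post-baseline abnormal result ends up under the current text.**

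| Result | Laboratory summary | TEAE tables by grade | Listing |
|---|---|---|---|
| Scheduled, judged clinically significant | yes, not as an incidence | yes | yes |
| Scheduled, not so judged | yes, not as an incidence | no | yes |
| Unscheduled, judged clinically significant | no | yes | yes |
| Unscheduled, not so judged | no | no | yes |

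The clinical-significance column follows Protocol 8.2; the TEAE column follows SAP 10.5.1. The last row is untabulated anywhere, and no row yields a count for the endpoint based on test results.

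**6. ECG.** SAP 10.1.1 defines a Part 2 baseline, and SAP 10.5.4 summarises vital-sign changes by part, but ECG change is summarised for Part 1 only and no reason is given. Appendix 4 schedules Part 2 ECGs at the predose and end-of-treatment visits only, and the latter can be skipped if one was done in the preceding 14 days. At most about one scheduled post-baseline change per patient goes unsummarised.

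**The case against.** **Adverse event tables already catch what matters.** Protocol 8.2 says clinically significant labs generally include those needing active treatment or leading to a dose hold, and Table 3 concerns related adverse events. SAP 10.5.1 tabulates these by part at maximum grade, whatever the timing of the sample. This largely stands for significant results. It does not dispose of the point: the protocol lists the two incidences separately and bases the laboratory one on test results, while recording as an adverse event rests on the investigator's judgment. Grade 2 neutropenia, for instance, has no row in Table 3 and need not prompt a hold.

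**Listings suffice at this size.** With up to about 10 patients, a reader can find each worst value, and the protocol synopsis allows safety data to be summarised and/or listed. This limits the harm, but a listing is not an incidence.

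**The table shells may hold the analysis.** They are a separate document that was not available for this review, so this cannot be excluded. SAP 10.1.2 would still strip unscheduled labs from such a table.

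**A stronger reading to avoid.** A reader might infer that Part 2 toxicity is understated, and size it by the chance that no scheduled lab falls within an abnormality: at 28-day gaps, 1 − 7/28 = 75% for an assumed 7-day nadir and 1 − 14/28 = 50% for 14 days. The documents do not support this. That chance is not the share found in unscheduled samples. If nothing prompts a draw, the value is never measured and no SAP wording recovers it. If an abnormal scheduled result prompts the draws, an abnormality is already in the summary. Nadir length is not given, dosing is continuous, and significant results reach the TEAE tables.

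**Conclusion.** The point holds. A named secondary endpoint has no analysis specified in the SAP, and a stated rule would remove unscheduled labs from one if it were added. Laboratory summaries may therefore miss transient or worst Part 2 values. It does not follow that toxicity as a whole is understated. The uncovered part is mainly abnormalities not reported as adverse events; its size cannot be computed from the documents, and no percentage should be attached to it.

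The conclusion rests on the SAP text without the table shells, and on the assumption that some labs will be drawn between visits, which the visit gaps, Table 3 and the blood allowance make likely. The ECG omission is minor. The effect is on descriptive safety reporting; the primary pharmacokinetic and mass-balance objectives are untouched.

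**What to change.** - **SAP 10.5.3:** for each gradable hematology and chemistry parameter, tabulate by part the number and percent of patients by worst post-baseline CTCAE grade, or by shift from baseline, including unscheduled results. State the CTCAE version, the denominator (patients in that part's Safety Population with a post-baseline value) and the period covered by each part.
- **SAP 10.1.2:** limit the exclusion of unscheduled readings to by-visit summaries.
- **SAP 10.5.5 (minor):** summarise ECG change from baseline for Part 2 as well, or state why it is omitted.
- **Table shells:** check that they match the revised wording.

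The cost is a few sentences in the SAP and one or two extra tables from data already collected. No visit, sample or protocol procedure changes. It should be settled before database lock.
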